3.3 Study Hypothesis

There are no statistical hypotheses to be tested.

3.4 Exploratory Endpoints

There are no exploratory analyses planned.

4 INVESTIGATIONAL PLAN

4.1 Overall Study Design and Plan

This is a single-center, open-label, concentration-ranging study to evaluate the nicotine PK profile and PD effects in healthy White adult experienced users of closed tank/cartridge e-cigarettes using four different variants of P4M3 or their own e-cigarettes.

A Screening Visit, including a demonstration of the P4M3 by the investigational site personnel, will be conducted within 3 weeks (Day -23 to Day -3) prior to Admission (Day -2) (see [Figure 1](#)).

On Day -2, subjects will be admitted to the investigational site at Admission. Subjects should have been fasting for at least 12 hours prior to Admission. After confirmation of subjects' eligibility, subjects will be enrolled in the study and have a debriefing on P4M3 followed by a product test with P4M3-1.7% *ad libitum* for a maximum of 10 minutes. After the product test, subjects not willing and/or not ready to use (e.g., intolerance) P4M3 will be discontinued and may be replaced. Subjects willing to continue will enter their confinement period of 6 days, from Day -2 to Day 5. Following the product test, subjects will be required to abstain from any nicotine/tobacco containing product use for at least 10 hours until the first product use on Day -1.

On Day -1 to Day 4, subjects will use either their own closed tank/cartridge e-cigarette/e-liquid or one P4M3 variant with two different regimens as described in [Figure 1](#):

- a fixed puffing regimen comprising of 12 puffs in total at a rate of one puff every 30 seconds (± 5 seconds) with HPT recording in the morning.
- *ad libitum* use for 60 minutes (± 5 minutes) with HPT recording in the afternoon

The start of product use of subjects' own e-cigarette and P4M3 variant (first puff) for fixed puffing and for the 60 minutes (± 5 minutes) *ad libitum* use will be defined as T0. T0 should be at approximately the same time (± 30 minutes) for fixed puffing in the morning and for *ad libitum* use in the afternoon for subjects' own e-cigarette on Day -1 (Baseline) and for P4M3 variants on Days 1 to 4. T0 for 60 minutes *ad libitum* use should be at least 10 hours after T0 for fixed puffing. There will be a washout of at least 10 hours following each *ad libitum* product use with respect to the subsequent fixed puffing regimen in the next morning to allow adequate background correction of the fixed puffing regimen-related nicotine plasma concentrations.

On Day -1 (Baseline), subjects will be instructed to use their own closed tank/cartridge e-cigarette with fixed puffing regimen in the morning and subsequently, to use it *ad libitum* for 60 minutes in the afternoon ([Figure 1](#)).

On Day 1, subjects will be randomized to one of two sequences of the P4M3 variants in order to cross-over the use of P4M3-1.7% and P4M3-1.7%LA:

Data and information contained in this document are considered to constitute trade secrets and confidential commercial information, and the legal protections provided to such trade secrets and confidential information are hereby claimed under the applicable provisions of US law. No part of this document may be publicly disclosed without the written consent of PMI.

Sequence 1:

P4M3-1.7%; P4M3-1.7 %LA; P4M3-3%LA; and P4M3-4%LA

Sequence 2:

P4M3-1.7%LA; P4M3-1.7 %; P4M3-3%LA; and P4M3-4%LA

On Days 1 to 4, subjects will be provided and instructed to use a new, ready-to-use product (full cartridge) of the assigned P4M3 variant for fixed puffing regimen with HPT recording in the morning and another new one for the *ad libitum* use for 60 minutes with HPT recording in the afternoon, according to one of two randomly assigned sequences. The concentration of P4M3 e-liquid will be the same on a given day for fixed puffing and *ad libitum* use on Days 1 to 4. During confinement, the use of nicotine/tobacco containing products other than the one allocated during the scheduled use periods will not be allowed.

Venous blood samples will be taken for analysis of PK parameters prior to the start of and during both fixed puffing and the 60 minutes *ad libitum* use at specified time points before and after T0 on Day -1 to Day 4. Blood sampling for the determination of nicotine and derived PK parameters will be collected for 4 hours following T0 of fixed puffing in the mornings and for 4 hours following T0 of *ad libitum* use in the afternoons.

[figure not shown]
On Day 5, subjects will remain in the study center for additional PK blood sampling up to 24 hours after T0 of the *ad libitum* session on Day 4 for the purposes of estimating the terminal elimination half-life.

Subjects will be discharged following completion of assessments at Day 5 and will enter a 7-day passive safety FU during which there will be recording of spontaneously reported new AE/SAEs and the active follow-up of ongoing AE/SAEs by the Investigator. Any non-serious AE that is ongoing during the passive safety FU will be actively followed up by the Investigator or designee during that period until it has been resolved, stabilized (i.e., no worsening of the condition), an acceptable explanation has been found (e.g., a chronic condition) or lost to follow-up. At the end of the passive safety FU, all ongoing non-serious AEs will be documented as “ongoing” and no follow-up information will be sought for them anymore by the Investigator or designee. At that point, the Investigator will assess whether the subject should be referred to his/her General Practitioner to have their ongoing AEs addressed accordingly. All SAEs will be followed up by the Investigator or designee, despite their continuation after the end of the passive safety FU, until their resolution, stabilization (i.e., no worsening of the condition), or an acceptable explanation has been found (e.g., a chronic condition). SAEs reported after the subject’s EOS that are considered related to P4M3 by the Investigator must be captured and reported to UBC/PMI regardless of time after EOS. The EOS for a subject is defined as his/her discharge on Day 5 or the date of early termination of the subject, plus 7 days of passive safety FU.

The study schematic is presented in [Figure 1](#). The schedule of events is provided in [Appendix 1](#).

Figure 1 Study Schematic

Data and information contained in this document are considered to constitute trade secrets and confidential commercial information, and the legal protections provided to such trade secrets and confidential information are hereby claimed under the applicable provisions of US law. No part of this document may be publicly disclosed without the written consent of PMI.

4.2 Rationale for Study Design

The goal of the study will be to select the P4M3 variant(s) that result(s) in nicotine absorption close to that observed with subjects' own e-cigarettes. The nicotine plasma concentration profiles and derived PK parameters, subjective and behavioral effects, and HPT parameters of P4M3 variants and subjects' own e-cigarettes will be evaluated. The concentrations of nicotine in some of the P4M3 variants tested in this study are already available on the market and exposure of the IPs will be to experienced e-cigarette users aged 21 - 65 years (inclusive) following a single-use experience with fixed puffing in the morning and after *ad libitum* use of P4M3 in the afternoon across 4 days. Subjects with a history of e-cigarette use were chosen for this study based on data from previous studies indicating that having previous experience using such products may impact nicotine exposure and puffing topography (Farsalinos 2013, 2015; Spindle 2015). Further, the use of fixed and *ad libitum* puffing regimens by experienced consumers is expected to provide insight into nicotine delivery by the products that is possible under consistent use conditions across subjects (fixed puffing regimen) as well as a means to assess the products' ability to meet a consumers needs during short-term "real-life" use conditions (*ad libitum* regimen).

Plasma nicotine presents a biphasic profile, with a typical rapid initial disposition half-life ($t_{1/2\alpha}$) of 1.35 hours, followed by a slower terminal elimination half-life ($t_{1/2z}$) of 17 hours (Marchand et al, 2017). To ensure a full nicotine washout between each product use, a separation of 3 days would be required ($\sim 5 \times$ elimination $t_{1/2z}$). Due to the impracticality of undergoing long periods of abstinence for smokers, shorter washout periods have been selected. To minimize the potential bias in the nicotine plasma PK parameters for the fixed puffing regimens, background-concentration correction will be applied to adjust for carry-over effects. The simplest approach by which this can be achieved requires a) a minimum washout-out period of 10 hours prior to each fixed puffing regimen session (this ensures that subjects have entered the terminal elimination phase of nicotine) and b) the estimation of $t_{1/2z}$ (or the terminal elimination rate constant λ_z) on Day 5 for each subject.

The use of estrogen-containing contraceptives is known to accelerate nicotine clearance by 20% to 30% in women as compared to women who do not take such contraceptives (Benowitz et al, 2006). Therefore, for the purpose of this study, it is not allowed to use hormonal contraception containing estrogen or hormone replacement therapy.

The activity of CYP2A6 will be measured at Admission as nicotine metabolism by CYP2A6 varies between individuals of the same ethnicity/race, and across ethnicity/race due to genetic variations. These genetic differences could be associated with reduced/increased nicotine metabolism (Hukkanen et al, 2005).

4.3 Study Duration

The entire study per subject will last between 15 to 36 days, including a Screening Visit of up to 3 weeks (Day -23 to Day -3) prior to Admission, 1 day of Admission (Day -2), 5 days of product use (Days -1 to 4), and 7 days of passive safety FU.

4.4 Appropriateness of Measurement

All laboratory measures utilized for this study are validated and are appropriate for the study assessments.

All questionnaires to be used during the study, with the exception of the cough questionnaire, are adapted versions of validated questionnaires.

4.5 Study Stopping Criteria

The study may be stopped if the subjects are placed at risk because of clinically significant findings or SAEs that, e.g.:

- are assessed as causally related to P4M3.
- are not considered to be consistent with continuation of the study
- are not consistent with the information provided in Section 6.5 of the current IB

The Sponsor, Investigator, and/or IRB reserve the right to terminate or suspend the study at any time; however this should be discussed between the relevant parties beforehand and the reason for such decision recorded. Should this occur, all data available will also be recorded in the case report forms (CRFs). The Investigator should notify the IRB in writing of the study's completion or early discontinuation.

In the event that the study is terminated early, every effort should be made by the Investigator, investigational site personnel, and Sponsor to follow AEs and SAEs for all subjects until the end of the passive safety FU.

5 STUDY POPULATION

5.1 Selection of Study Population

Sixteen (16) White female or male healthy adult subjects who have used e-cigarettes daily for at least 3 months prior to the Screening Visit will be enrolled into this study. The e-cigarette use status of the subjects will be verified based on a urine cotinine test (cotinine \geq 200 ng/mL).

5.1.1 Inclusion Criteria

Inclusion Criteria	Rationale	Screening	Day of Admission (Day -2)
1. Subject has signed the ICF and is able to understand the information provided in the ICF.	Administrative	X	
2. Subject is aged from 21 to 65 years, inclusive, at the Screening Visit.	Safety	X	
3. Subject is White.	Effect	X	
4. Subject is a former daily cigarette smoker who smoked at least 100 cigarettes or more in his/her life and ceased smoking at least 3 months prior to the Screening Visit.	Safety	X	
5. Subject has been using a commercially available, nicotine-containing closed tank/cartridge e-cigarette daily for at least 3 months prior to the Screening Visit.	Effect	X	
6. Subject has a urine cotinine test \geq 200 ng/mL at the Screening Visit and Admission.	Effect	X	X
7. Subject does not plan to quit using e-cigarettes during the study.	Effect	X	X
8. Subject is ready to comply with study procedures.	Effect	X	X

Data and information contained in this document are considered to constitute trade secrets and confidential commercial information, and the legal protections provided to such trade secrets and confidential information are hereby claimed under the applicable provisions of US law. No part of this document may be publicly disclosed without the written consent of PMI.

Inclusion Criteria	Rationale	Screening	Day of Admission (Day -2)
9. Subject is ready to accept periods of interruption of nicotine use.	Effect	X	X
10. Subject is ready to accept using the P4M3 product variants as instructed and for the duration of the study.	Effect	X	X

5.1.2 Exclusion Criteria

Subjects who meet any of the following exclusion criteria must not be enrolled into the study:

Exclusion Criteria	Rationale	Screening	Day of Admission (Day -2)
1. Subject has a clinically relevant disease which requires medication (including but not limited to gastrointestinal, renal, hepatic, neurological, hematological, endocrine, oncological, urological, immunological, pulmonary, and cardiovascular disease or any other medical condition (including safety laboratory as per CTCAE), which as per the judgment of the Investigator would jeopardize the safety of the subject).	Safety	X	X
2. Subject has abnormal renal function test result or subject with a creatinine clearance <60 mL/minute (as determined by the Cockcroft-Gault) at the Screening Visit, confirmed on repeat testing.	Safety	X	
3. Subject has elevated liver function test results (ALT or AST >2X ULN) at the Screening Visit.	Safety	X	

Data and information contained in this document are considered to constitute trade secrets and confidential commercial information, and the legal protections provided to such trade secrets and confidential information are hereby claimed under the applicable provisions of US law. No part of this document may be publicly disclosed without the written consent of PMI.

Exclusion Criteria	Rationale	Screening	Day of Admission (Day -2)
4. Subject has bilirubin >1.5X ULN (isolated bilirubin >1.5X ULN is acceptable if bilirubin is fractionated and direct bilirubin <35%) at the Screening Visit.	Safety	X	
5. Subject has FEV ₁ /FVC <0.7 and FEV ₁ <80% predicted value at post-bronchodilator spirometry at the Screening Visit.	Safety	X	
6. Subject has asthma condition (FEV ₁ /FVC <0.75 and reversibility in FEV ₁ >12% and > 200 mL from pre- to post-bronchodilator values) at the Screening Visit.	Safety	X	
7. Subject has received medication (prescription or over-the-counter) within 14 days or within 5 half-lives of the drug (whichever is longer) prior to Admission which has an impact on CYP2A6 activity (See Table 1).	Safety		X
8. Subject has a CO breath test \geq 10 ppm at the Screening Visit or Admission.	Effect	X	X
9. Subject has a positive alcohol test at the Screening Visit or Admission and/or the subject has a history of alcohol abuse that could interfere with the subject's participation in study.	Administrative	X	X
10. Subject has a positive urine drug screen at the Screening Visit or Admission.	Administrative	X	X
11. Subject has a BMI <18.5 kg/m ² or BMI \geq 35 kg/m ² at the Screening Visit.	Safety	X	

Data and information contained in this document are considered to constitute trade secrets and confidential commercial information, and the legal protections provided to such trade secrets and confidential information are hereby claimed under the applicable provisions of US law. No part of this document may be publicly disclosed without the written consent of PMI.

Exclusion Criteria	Rationale	Screening	Day of Admission (Day -2)
12. Subject has a positive serology test for HIV 1/2, hepatitis B, or hepatitis C at the Screening Visit.	Administrative	X	
13. The subject has a baseline QTcF >450 ms for males or >470 ms for females at the Screening Visit or history of congenital long QT syndrome, or Torsades de Pointes.	Safety	X	
14. Subject has abnormal (clinically significant) ECG findings at the Screening Visit. Entry of any subject with an abnormal (not clinically significant) ECG must be approved, and documented by signature by the Investigator.	Safety	X	
15. Subject or one of their family members* is a current or former employee of the tobacco industry.	Administrative	X	
16. Subject or one of their family members* is an employee of the investigational site or any other parties involved in the study.	Administrative	X	
17. Subject has participated in a clinical study within 3 months prior to the Screening Visit.	Safety	X	
18. Subject has been previously screened in this study and failed to meet the eligibility criteria.	Administrative	X	

Data and information contained in this document are considered to constitute trade secrets and confidential commercial information, and the legal protections provided to such trade secrets and confidential information are hereby claimed under the applicable provisions of US law. No part of this document may be publicly disclosed without the written consent of PMI.

Exclusion Criteria	Rationale	Screening	Day of Admission (Day -2)
19. Subject smokes combustible cigarettes or other tobacco products (with the exception of commercially available, nicotine containing closed tank/cartridge e-cigarette).	Effect	X	X
20. Subject is using estrogen-containing medication.	Effect	X	X
21. Female subject of childbearing potential who is pregnant or breastfeeding.	Safety	X	X
22. Female subject of childbearing potential who does not agree to use an acceptable method of effective contraception**. Female subject who is not of childbearing potential must meet at least one of the following criteria: - has undergone hysterectomy or bilateral tubal ligation, - has medically confirmed ovarian failure, or - is medically confirmed to be postmenopausal (cessation of regular menses for at least 12 consecutive months prior to Admission with no alternative pathological or physiological cause).	Safety	X	X

* As defined by the FDA guidance Human Subject Protection (21 CFR 50.3(l), (m), 50.24(a)(6), (a)(7)(v), b)).

"Family member" means among other things "parent", "spouse", "brothers, sisters, and spouses of brothers and sisters" and "any individual related by affinity whose close association with the subject is equivalent of a family relationship"

**Acceptable methods of effective contraception:

Intrauterine device, intrauterine system, barrier methods of contraception (condoms, occlusive caps) with spermicidal foam/gel/film/suppository, hormonal contraception containing progesterone only, vasectomized partner(s), or true abstinence (periodic abstinence and withdrawal are not effective methods) from the Screening Visit until the end of the passive safety FU. Hormonal contraception with estrogen containing products is NOT allowed in this study.

Data and information contained in this document are considered to constitute trade secrets and confidential commercial information, and the legal protections provided to such trade secrets and confidential information are hereby claimed under the applicable provisions of US law. No part of this document may be publicly disclosed without the written consent of PMI.

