6.3.1 Admission (Day -2)

Subjects will be admitted to the investigational site at Admission (Day -2) for assessments and a debriefing on P4M3. Subjects should have been fasting for at least 12 hours prior to Admission. After confirmation of subjects' eligibility, subjects will be enrolled in the study, have a debriefing on

P4M3, and perform a product test with P4M3-1.7% for a maximum of 10 minutes. The product test will be physically connected to the puffing topography device without recording of parameters (HPT device switched off). After the product test, subjects not willing and/or ready to use P4M3 will be discontinued and may be replaced. Following the product test, subjects will be required to abstain from any nicotine/tobacco containing product use for at least 10 hours until the first product use on Day -1.

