7.5.8 Urine Pregnancy Testing

All female subjects will have urine pregnancy testing at the Screening Visit, at Admission, and at the Day of Discharge (Day 5) or early termination. Female subjects with a positive pregnancy test at the Screening Visit or on Day -2 cannot be enrolled and are considered a screening failure. Pregnancy in such subjects will not be followed up as no exposure to the P4M3 IP will have occurred. In any case of a positive pregnancy test, the Investigator will inform the subject about the risks associated with nicotine/tobacco use during pregnancy.

All pregnancies detected during the study must be reported and handled as described in [Section 8.5](#).

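### Exclusion criterion 21 ties the breastfeeding exclusion to childbearing potential, so a breastfeeding woman after tubal ligation or hysterectomy is not excluded as written

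*Protocol*

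**What the plan says.** Criterion 21 in Section 5.1.2 excludes a "Female subject of childbearing potential who is pregnant or breastfeeding". The table gives safety as the rationale and has the criterion checked at both Screening and Admission. The synopsis carries the same sentence with the same qualifier.

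Criterion 22, which deals with contraception, adds: "Female subject who is not of childbearing potential must meet at least one of the following criteria". The first condition listed is that she "has undergone hysterectomy or bilateral tubal ligation"; the others are confirmed ovarian failure and confirmed postmenopausal status.

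Section 7.5.8 takes a wider scope for pregnancy: "All female subjects will have urine pregnancy testing at the Screening Visit, at Admission", and again at discharge or early termination. It goes on: "Female subjects with a positive pregnancy test at the Screening Visit or on Day -2 cannot be enrolled and are considered a screening failure". It makes no reference to childbearing potential.

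After enrolment on Day -2, Section 6.3.1 has each subject "perform a product test with P4M3-1.7% for a maximum of 10 minutes". Own-product use follows on Day -1 and P4M3 use on Days 1 to 4.

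**The concern.** The qualifier in criterion 21 governs both pregnancy and breastfeeding. For contraception, the subject of criterion 22, childbearing potential is the natural dividing line. For breastfeeding it is not: a woman can have a tubal ligation or a hysterectomy and still be breastfeeding. So the exclusion lapses in a group where the condition it targets can still occur, and nothing in the protocol suggests that the sponsor meant it to lapse there.

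At stake is whether a safety exclusion that the sponsor chose to write works as intended. A site working from a checklist built on this text would have no written ground to exclude such a woman. Nothing statistical is at stake: no endpoint, estimand, model or sample size depends on it.

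**Working it through.** No arithmetic is needed for the main point. It is a check of the eligibility logic.

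**1. Criterion 21 as a rule.** Exclude if (childbearing potential) AND (pregnant OR breastfeeding).

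**2. A breastfeeding woman with bilateral tubal ligation or hysterectomy, not pregnant.**

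| Provision | Outcome |
|---|---|
| Criterion 22, listed conditions | She meets one, so she counts as not of childbearing potential and is not excluded by criterion 22 |
| Criterion 21 | First condition false, so not excluded |
| Section 7.5.8 | Pregnancy test negative, so not excluded |
| Criterion 1 | Concerns disease or another medical condition "which as per the judgment of the Investigator would jeopardize the safety of the subject"; it names neither breastfeeding nor an infant |

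Result: if the remaining criteria are satisfied, the text lets her be enrolled.

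**3. A pregnant woman classed as not of childbearing potential.** Criterion 21 misses her, but under Section 7.5.8 the positive test makes her a screening failure. Section 8.5.1 treats a pregnancy found before first product exposure as a screen failure, and Section 5.1.3 requires discontinuation on a positive test. Result: she is kept out. There is no gap for pregnancy.

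**4. Search for another bar on breastfeeding.** Places read: the inclusion criteria (5.1.1), the other exclusion criteria (5.1.2), the discontinuation rules (5.1.3), the product and dietary restrictions (6.7), the Screening and Admission schedules (Tables 5 and 6) and Appendix 1. None mentions breastfeeding. The best-interest clause in Section 5.1.3 covers the subject and the other subjects, not an infant. Breastfeeding appears only in criterion 21 and its synopsis copy.

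**5. Size.**
- Women among those randomised: at least 5 of each sex out of 16 (synopsis), so between 5 and 16 − 5 = 11 women. The protocol gives no rate for being both surgically sterile and breastfeeding. Assumption: 0 to 1 subject.
- Product use for such a subject: two regimens a day on five days (Day -1 and Days 1 to 4) gives 5 × 2 = 10 sessions. The two on Day -1 use her own e-cigarette, which leaves 4 × 2 = 8 P4M3 sessions, plus the product test of at most 10 minutes. In both sequences the 4% variant comes last, on Day 4, so it accounts for 2 of the 8.

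**The case against.** Several points can fairly be made against giving this much weight.

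- **Pregnancy.** A reader might infer from criterion 21 that pregnant women of non-childbearing status can enter, or that criterion 21 contradicts Section 7.5.8. The protocol does not support either reading. Section 7.5.8 adds a wider bar on top of criterion 21, and no subject receives two opposite instructions. This objection stands in full, and the point is limited to breastfeeding.
- **Exposure.** A reader might picture several days on the 4% product. It is used on Day 4 only, and two of the ten sessions are with the subject's own device. This also stands.
- **Background use.** Every eligible subject has used a nicotine e-cigarette daily for at least 3 months, has urine cotinine of at least 200 ng/mL and does not plan to quit during the study (inclusion criteria 5 to 7). During confinement nicotine is limited to scheduled sessions; after discharge subjects may return to their usual habits (Section 6.3.4). Whether participation raises or lowers such a woman's nicotine intake cannot be worked out from the protocol. That stands as a limit on any claim of harm. It does not justify the gap, because it applies equally to the breastfeeding women whom criterion 21 does exclude.
- **Infant harm.** A reader might infer a demonstrated risk to an infant after discharge. The protocol says nothing about nicotine in milk or whether breastfeeding would continue during confinement, and the last blood sample before discharge is 24 hours after the start of the last use. What the protocol does show is that the sponsor classed breastfeeding as a safety exclusion.
- **Reading of criterion 22.** Strictly, it states a necessary condition for being not of childbearing potential, not a definition. Reading it as the definition is the natural course. If it is not one, the scope of criterion 21 is left to each reader, which is no improvement.
- **Investigator judgement.** The investigator may well decline to enrol such a woman. That is plausible, but criterion 1 is framed around the subject's own safety and does not reliably cover the case.

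**Conclusion.** Wrong as written, minor. A stated safety exclusion, followed literally, omits breastfeeding women who have had a hysterectomy or bilateral tubal ligation, and no other provision catches them. The conclusion rests on reading the criterion 22 list as defining who is not of childbearing potential, and on the plain fact that neither operation stops breastfeeding.

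The likely number affected is 0 to 1 of 16, which is an assumption and not a figure from the protocol. Pregnant women are fully covered elsewhere. No increase in nicotine exposure over the subject's habitual use is shown, and no analysis or result is affected.

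**What to change.** Reconcile the scope of criterion 21 with criterion 22 and with the all-female scope of Section 7.5.8, so that the breastfeeding exclusion does not depend on childbearing potential. One way is to remove that qualifier from criterion 21. Make the change in Section 5.1.2 and in the synopsis, and carry it into any eligibility checklist built from them. The contraception requirement in criterion 22 can keep its present scope.

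The cost is a few words in two places at the next amendment. Sample size, visit schedule, procedures and statistical analysis stay as they are.
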